10. STUDY CALENDAR

Notations/reminders for all calendars:

- Baselines assessments are to be conducted within 7 days prior to start of protocol therapy unless otherwise noted. If the patient will receive pre-phase treatment, then a BM aspirate and biopsy within 14 days of starting treatment on this study is allowed.
- On study physical exams to include medical history since last assessment, as appropriate.
- Pregnancy test (serum or urine) is required for women of childbearing potential ≤ 3 days prior to study enrollment and must be negative to initiate treatment.
- Correlative blood and bone marrow sample participation is mandatory.
- Additional tests may be performed at the discretion of the treating investigator or site as per routine practice, or as otherwise clinically indicated.
- The schedule should be followed as closely as is realistically possible; however, the schedule may be modified due to problems such as scheduling delays or conflicts (e.g., clinic closure, poor weather conditions, vacations, etc.) with the guidance of the Protocol Chair/designee, as appropriate, and will not be reportable as a deviation unless the endpoints of the study are affected.

Table 10.1	Screening	Cycle 1			Cycles 2-5			Beyond Cycle 5		
Treatment Cycle:	Main Study Screening	Week1	Weeks 2-4	Weeks 5-6	Week 1	Weeks 2-4	Weeks 5-6	Every 2 weeks for up to 1 year	Every 3 months for 2 years after completing study treatment	Off Study
Blinatumomab (D 1-28 every 42 days)		X	X		X (D1-D28)	X (D1-D28 only)				
Nivolumab (every 2 weeks starting on D11 of Cycle 1) ¹			X	X		X	X	X		
Ipilimumab (every 6 weeks starting on D11 of Cycle 1) ¹			X			X		X (Every 6 weeks)		
Informed Consent	X									
Inclusion/Exclusion Criteria	X									
Demographics and Medical History	X									
Concurrent Meds	X	X-----X								
History/Physical Exam ²	X	X	X	X	X	X	X	X	X	X
Vital Signs including oxygen saturation ²	X	X	X	X	X	X	X	X	X	
Height/Weight ²	X	X			X			X (every 6 weeks)		
Performance Status ²	X	X			X			X (every 6 weeks)		
CBC with	X	X	X	X	X	X		X	X	X

Differential ³										
PT, aPTT, fibrinogen, D-dimer ⁴	X	X	X		X					
Serum chemistry ⁵	X	X	X	X	X	X	X	X	X	X
Amylase, lipase ⁶	X		X	X		X	X	X		
TSH (with reflective Free T3 and FreeT4) ⁶	X		X	X		X	X	X		
Hepatitis Serologies ⁷	X									
Quantitative Immunoglobulin ⁸	X				X ⁸ (cy 2 only)		X ⁸ (end of cy 5)	X ⁸ (every 3-6 months)	X ⁸ (every 3-6 months)	
Urinalysis	X									
Serum or urine HCG for WOCBP only ⁹	X				X			X (every 6 weeks)		
Writing Test ¹⁰	X	X	X		X	X ¹⁰				
EKG ¹¹ and ECHOcardiogram	X									
BM Aspirate and Biopsy ¹²	X		X (within 3 days prior to 1 st nivolumab)	X			X ¹² (end Cy 2; every 3-4 mos up to 1 year)	X ¹² (every 3-4 months up to 1 year)		X ¹² (off treatment or relapse)
MRD Monitoring ¹²	X		X	X			X ¹²	X ¹²		X
LP and CSF analysis with Intrathecal Chemotherapy ¹³	X			X			X ¹³ (cy 2 only required)	As per investigator's discretion	As per investigator's discretion	

Correlative Studies from BM (Section 9.1 and Appendix E for instructions) ¹⁴	X		X (within 3 days prior to nivo)	X			X ¹⁴	X ¹⁴		X ¹⁴
Correlative Studies from PB (Section 9.1 and Appendix E for instructions) ¹⁵	X	X	X	X	X	X	X	X (every 3-4 months up to 1 year)		X ¹⁵ (off treatment or relapse)
Symptom/Toxicity Assessment ¹⁶	X	X-----X ¹⁶ See specific requirements for monitoring after last dose of nivolumab and/or ipilimumab, and after allo-HSCT ¹⁶								
Follow-up/Survival ¹⁷									X ¹⁷	X ¹⁷

¹ Ipilimumab will be administered every 6 weeks and only to subjects treated on DL B1 (B-1) and B-2. Both Ipilimumab and Nivolumab can be given ± 2 days from the scheduled time and delayed in Cycle 1 up to day 25 as defined in Section 5.3.2 and 5.3.3.
 
² Interim history/physical exam and vital signs (heart rate, blood pressure, temperature, respiratory rate and O2 saturation) will be performed prior to each cycle, weekly during cycle 1 and 2, and every 2 weeks in cycle ≥3. During cycle 1 patient are expected to be hospitalized for 14 days and in subsequent cycles for the first 2 days and will have daily history/physical exam/vital signs (including S02) as per standard of care (SOC). Vital signs (including S02) will be monitored prior to start of each nivolumab and ipilimumab infusion and at the end of infusion or more frequently as indicated. Height will be recorded only prior to start of treatment on the study. Weight and performance status will be measured/assessed prior to each cycle (every 6 weeks).
 
³ CBC and differential will be performed on day 1 of each cycle, daily for the first 4 days of cycle 1, weekly during cycle 1 and 2, and every 2 weeks thereafter for the duration of therapy. CBC and diff should be performed within three days of nivolumab and ipilimumab administration. The frequency of CBC/diff measurements may be higher and adjusted for individual patient’s need as per the SOC requirements for monitoring and treatment of patients with ALL.
										

⁴ PT/PTT, fibrinogen and d-dimer will be measured prior to each cycle of blinatumomab. In cycle 1, due to higher risk for DIC because of active disease, PT/PTT, fibrinogen and d-dimer should be checked at least twice a week in the first two weeks. The frequency of measurement may be higher and adjusted for individual patient's need as per the SOC requirements for monitoring and treatment of patients with ALL.

⁵ Serum chemistry: albumin, alkaline phosphatase, total bilirubin, bicarbonate, BUN, calcium, chloride, creatinine, glucose, LDH, phosphorus, potassium, total protein, SGOT [AST], SGPT [ALT], sodium, uric acid. Serum chemistry will be performed on day 1 of each cycle, daily for the first 4 days of cycle 1, weekly during cycle 1 and 2, and every 2 weeks thereafter for the duration of therapy. Serum chemistry should be performed within three days of nivolumab and ipilimumab administration. The frequency of serum chemistry measurements may be higher and adjusted for individual patient's need as per the SOC requirements for monitoring and treatment of patients with ALL.

⁶ Amylase, lipase, and TSH should be checked within three days prior to each nivolumab administration. If TSH is abnormal, Free T3 (triiodothyronine) and T4 (thyroxine) should be assessed. Screening time point must be done within 28 days of registration.

⁷ Hepatitis serologies will be performed as baseline and include: Hepatitis B surface antigen (HBV sAg), Hepatitis B core antibody (anti-HBc), and Hepatitis surface antibody (HBsAb). Hepatitis C antibody (HCV Ab) and/or Hepatitis C RNA (HCV RNA). Screening time point must be done within 28 days of registration.

⁸ Quantitative immunoglobulin should be measured at baseline, at the end of cycle 1, at the end of the last blinatumomab cycle and every 3-6 months thereafter until off study. Screening time point must be done within 28 days of registration.

⁹ For WOCBP (women of childbearing potential) only: A serum or urine pregnancy testing is required prior to study enrollment and prior to each cycle.

¹⁰ Writing test (Appendix G) should be performed at baseline, prior to each cycle, and then weekly during blinatumomab administration (week1-4) in cycle 1 and 2 and every 2 weeks during blinatumomab administration (week 1-4) in cycle ≥ 3 of blinatumomab.

¹¹ All patients should have baseline ECG. Baseline ECHOCardiogram is required for patients with a history of CHF, or at risk because of underlying cardiovascular disease (e.g history of angina, heart attack, or prior cardiovascular interventions or findings), history of cardiac arrhythmias, or exposure to cardiotoxic drugs (e.g anthracyclines, cyclophosphamide, or others) as clinically indicated. Any patient with heart arrhythmia or ischemic changes on baseline ECG should have baseline ECHOCardiogram. In addition, any patient who develop symptoms or signs of CHF, MI, cardiomyopathy, or myositis in the course of the study, should have repeat EKG, ECHOCardiogram, as well as cardiac evaluation including lab tests, CPK, troponin, and cardiology consultations as clinically indicated.

¹² Bone marrow aspirate and biopsy to assess disease status and response to therapy will be performed at baseline (after pre-registration and prior to registration), at the end of cycle 1 and 2 (day 29-day 35), and every 3-4 months thereafter up to 1 yr, any time relapse is suspected or off treatment. Additional bone marrow aspirates for research purposes only will be performed in cycle 1 within 3 days of the first nivolumab/ipilimumab administration (between days 8-11 of cycle 1 but can be delayed if nivolumab and/or ipilimumab administration is delayed in Cycle 1 as per Section 5.3.2 and 5.3.3) prior to nivolumab administration. Each time bone marrow assessment is performed to assess disease status, the flow cytometry studies for MRD assessment will be performed.

¹³ All patients should have baseline CSF assessment prior to enrollment on the study. Administration of intrathecal chemotherapy is required when LP is performed with a choice of agent (ara-C or MTX or both) and dose as per institutional standard of practice. Subsequent IT chemotherapy administration for CNS prophylaxis should be performed at the end of blinatumomab administration in cycles 1 and 2 (day 29-35) and the determination of need for subsequent CSF prophylaxis will be per investigator's discretion.

¹⁴ Each time bone marrow is performed for disease status assessment additional 40 cc of the bone marrow should be collected for research studies. Additional bone marrow aspirate for research purpose only will be performed in cycle 1 (between days 8-11) prior to nivolumab administration.

¹⁵ Peripheral blood 100 cc (min 60 cc) for research studies will be collected at baseline (after pre-registration and prior to registration), prior to first dose of nivolumab / ipilimumab in cycle 1 (-3 days), at the end of cycle 1 and 2 (day 29-35), and every 3-4 months up to 1 yr, or at the time of relapse or off treatment. Additional research peripheral blood 40 cc (min 30 cc) will be collected in cycle 1 (day 1, 15, 22; all ± 3 days), on day 1 (-3 days) of cycle 2.

¹⁶ Assessments for toxicity/adverse events are to continue for 100 days after the last dose of nivolumab or ipilimumab, whichever was administered last. These may occur by phone for subjects no longer being seen at the institution; however, an in-person clinic visit may be needed to confirm event resolution and/or to effectively evaluate possible immune-related events. In addition, all patients who go onto allo-HSCT following the completion of treatment on the study will undergo continuous monitoring for acute grade 3-4 graft versus host disease and post-transplant non-relapse mortality for the first 100 post-transplant days. Subjects must be told of follow-up requirements at study entry.

¹⁷ Subjects will be followed about every 3 months for disease status and survival. Information about subsequent treatment received and response will be collected.

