- total bilirubin ≤ 2.0 mg/dL (except patients with Gilbert Syndrome, who can have total bilirubin < 3.0 mg/dL)
 - AST(SGOT)/ALT(SGPT) $\leq 5 \times$ ULN
 - Serum creatinine $\leq 1.5 \times$ ULN
- OR
- creatinine clearance (CrCl) ≥ 50 mL/min (if using the Cockcroft-Gault formula below):

Female CrCl = $\frac{(140 - \text{age in years}) \times \text{weight in kg} \times 0.85}{72 \times \text{serum creatinine in mg/dL}}$

Male CrCl = $\frac{(140 - \text{age in years}) \times \text{weight in kg} \times 1.00}{72 \times \text{serum creatinine in mg/dL}}$

3.2.10 The effects of nivolumab, ipilimumab, and blinatumomab on the developing human fetus are unknown. For this reason, women of child-bearing potential (WOCBP) and men must agree to use adequate contraception (hormonal or barrier method of birth control; abstinence) prior to study entry and for the duration of study participation. WOCBP should use an adequate method to avoid pregnancy for 23 weeks after the last dose of investigational drug. Women of childbearing potential must have a negative serum or urine pregnancy test (minimum sensitivity 25 IU/L or equivalent units of HCG) within 24 hours prior to the start of treatment on the study. Women must not be breastfeeding. Men who are sexually active with WOCBP must use any contraceptive method with a failure rate of less than 1% per year. Men receiving nivolumab \pm ipilimumab and blinatumomab and who are sexually active with WOCBP will be instructed to adhere to contraception for a period of 31 weeks after the last dose of investigational product. Women who are not of childbearing potential (*i.e.*, who are postmenopausal or surgically sterile as well as azoospermic men) do not require contraception.

Note: Women of childbearing potential (WOCBP) is defined as any female who has experienced menarche and who has not undergone surgical sterilization (hysterectomy or bilateral oophorectomy) or who is not postmenopausal. Menopause is defined clinically as 12 months of amenorrhea in a woman over 45 in the absence of other biological or physiological causes. In addition, women under the age of 55 must have a documented serum follicle stimulating hormone (FSH) level less than 40 mIU/mL.

Should a woman become pregnant or suspect she is pregnant while she or her partner is participating in this study, she (or the participating partner) should inform the treating physician immediately.

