4.3.3 OPEN/IWRS User Requirements

OPEN/IWRS users must meet the following requirements:

- Have a valid CTEP-IAM account (*i.e.*, CTEP username and password).
- To enroll patients or request slot reservations: Be on an ETCTN Corresponding or Participating Organization roster with the role of Registrar. Registrars must hold a minimum of an AP registration type.
- To approve slot reservations or access cohort management: Be identified to Theradex as the "Client Admin" for the study.
- Have regulatory approval for the conduct of the study at their site.

Prior to accessing OPEN/IWRS, site staff should verify the following:

- All eligibility criteria have been met within the protocol stated timeframes.
- If applicable, all patients have signed an appropriate consent form and HIPAA authorization form.

4.4 **General Guidelines**

Following registration, patients should begin protocol treatment as rapidly as possible. Issues that would cause treatment delays should be discussed with the Principal Investigator. If a patient does not receive protocol therapy following registration, the patient's registration on the study may be canceled. The Study Coordinator should be notified of cancellations as soon as possible.

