5.6 Duration of Therapy

In general, treatment may continue for up to 5 cycles of blinatumomab and up to 1 year of nivolumab/ipilimumab or until one of the following criteria are met:

- Disease relapse, progression, or a lack of a complete remission by the end of the 2nd cycle of treatment
- Intercurrent illness that prevents further administration of treatment
- Adverse event(s) which require(s) permanently going off study treatment (see also Section 6 and specific algorithms in Appendix D):
Any dosing interruption lasting >6 weeks for nivolumab or ipilimumab or >2 weeks for blinatumomab, with the following exceptions:
 - Dosing interruptions that occur for non-drug-related reasons may be allowed if approved by the Investigator. Prior to re-initiating treatment in a subject with a dosing interruption lasting greater than the specified time intervals, the Principal Investigator must be consulted. Tumor assessments should continue as per protocol even if dosing is interrupted.
- Dosing with blinatumomab, nivolumab and/or ipilimumab may be individually held or discontinued with other study treatment(s) continuing if drug-related toxicity can be definitively attributed to an agent(s) and other individual agent re-treatment criteria are met as outlined in Sections 6.2.1, 6.3.1., and 5.9. Patient decides to withdraw from the study
- General or specific changes in the patient's condition render the patient unacceptable for further treatment in the judgment of the investigator.
- Pregnancy
 - All WOCBP should be instructed to contact the investigator immediately if they suspect they might be pregnant (e.g., missed or late menstrual period) at any time during study participation. Institutional policy and local regulations should determine the frequency of on study pregnancy tests for WOCBP enrolled in the study.
 - The investigator must immediately notify CTEP in the event of a confirmed pregnancy in a subject participating in the study.
- Initiation of breast feeding by the patient
- Subject non-compliance
- Treatment required with other chemotherapeutic, investigational anti-neoplastic drugs, or allogeneic hematopoietic stem cell transplant. Patients should be off nivolumab therapy for at least 6 weeks prior to having allogeneic stem cell transplant.
- Delay of blinatumomab for more than 14 days within a cycle due to unresolved toxicities or delay of nivolumab or ipilimumab for more than six weeks due to unresolved toxicities.
- Death or lost for follow-up

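### The study calendar clears a patient for treatment on a pregnancy test up to 3 days before enrollment, while section 3.2.10 requires one within 24 hours before treatment

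*Combined protocol and SAP*

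**What the plan says.** Five places in the combined protocol and SAP bear on the timing of the pregnancy test.

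- **Section 3.2.10 (eligibility).** The negative serum or urine test must fall "within 24 hours prior to the start of treatment on the study". The anchor is the start of treatment.
- **Section 10, general notes to the calendar.** The test "is required for women of childbearing potential ≤ 3 days prior to study enrollment and must be negative to initiate treatment". The anchor is enrollment, and this is the test named as clearing the patient for treatment.
- **Table 10.1, HCG row.** Marks stand at screening, at week 1 of Cycles 2-5, and every 6 weeks beyond Cycle 5. All three Cycle 1 cells are empty.
- **Section 10, footnote 9.** "A serum or urine pregnancy testing is required prior to study enrollment and prior to each cycle". No number of hours or days is given.
- **Section 5.6.** "Institutional policy and local regulations should determine the frequency of on study pregnancy tests", which is not the same as footnote 9's test before every cycle.

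On the step from registration to first dose, section 4.3.3 has sites confirm before they use the enrollment system that "All eligibility criteria have been met within the protocol stated timeframes". Section 4.4 adds: "Following registration, patients should begin protocol treatment as rapidly as possible". It gives no maximum interval.

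**The concern.** Sites schedule procedures from the calendar. A site that does so here sees a test tied to enrollment, reads that this test has to be negative before treatment, finds no HCG mark in Cycle 1, and has no prompt to repeat the test before blinatumomab starts. The result can be a first dose given on a test that is out of date under 3.2.10.

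The stake is fetal exposure. Section 3.3.9 excludes pregnant women because nivolumab and ipilimumab may be teratogenic or abortifacient, and says that the same risks may hold for blinatumomab. Section 8.1.1 advises against blinatumomab in pregnancy. Required contraception (3.2.10) lowers the risk but does not replace the test. A lesser cost is an avoidable eligibility deviation at a site that followed the calendar in good faith.

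**Working it through.** The plan states no figure to reproduce. The check compares the texts and then works out how old a test can be.

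**1. The two windows**

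| Source | Longest allowed interval | Counted back from |
|---|---|---|
| 3.2.10 | 24 hours (1 day) | start of treatment |
| Calendar note | 3 days | enrollment |

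**2. Whether the grid supplies a Cycle 1 test.** It does not. The height/weight and performance status rows are a useful comparison: footnote 2 also places weight and performance status before each cycle, and both rows carry a mark in Cycle 1 week 1. The HCG row, under the same kind of footnote, does not. The inclusion/exclusion row is marked only at screening, so the calendar does not send the site back to 3.2.10 on Day 1.

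**3. Whether footnote 9 supplies it.** Only in part. Read literally, a test before each cycle includes Cycle 1. With no window, though, the enrollment test also precedes Cycle 1 and satisfies the words.

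**4. Whether the registration check supplies it.** Not reliably. The check in 4.3.3 comes before registration. If dosing follows more than 24 hours later, the 3.2.10 window has not yet opened when the check is made.

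**5. Age of the test at first dose.** Let *g* be the number of days from enrollment to first dose. The protocol gives no value or upper limit for *g*, so the values below are assumptions.

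Maximum age under the calendar note = 3 + *g* days. Excess over 3.2.10 = 3 + *g* − 1 = 2 + *g* days.

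| Assumed *g* (days) | Maximum age (days) | Limit in 3.2.10 (days) | Excess (days) |
|---|---|---|---|
| 0 | 3 + 0 = 3 | 1 | 2 |
| 1 | 3 + 1 = 4 | 1 | 3 |
| 3 | 3 + 3 = 6 | 1 | 5 |
| 7 | 3 + 7 = 10 | 1 | 9 |

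The calendar also has a general limit: "Baselines assessments are to be conducted within 7 days prior to start of protocol therapy unless otherwise noted". If it is taken to cover this test, the age cannot exceed 7 days. That cap is reached at *g* = 7 − 3 = 4, and the last row becomes 7 days with an excess of 6. The pregnancy test has its own note, however, so the general limit arguably does not apply.

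**6. Whether one test can meet both rules.** A test done before enrollment is at least *g* days old at first dose. If *g* is more than 1 day, no pre-enrollment test can satisfy 3.2.10 and a second test is needed. The calendar does not schedule that second test explicitly.

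**The case against.** The best reply is that the rules add to each other and do not contradict. Section 3.2.10 is a mandatory criterion and nothing in the calendar waives it. A site can meet both by repeating the test, or by timing one test inside both windows when dosing follows enrollment closely. On this view, dosing on a test older than 24 hours is a site deviation and not something the protocol permits. Footnote 9 does call for testing before each cycle, and the HCG row carries its marker. Blank cells in Table 10.1 are weak evidence, because the grid is untidy elsewhere: footnote 3 wants weekly blood counts through Cycle 2, yet the CBC row is blank for weeks 5-6 of Cycles 2-5. Treatment starts in hospital with Day 1 bloods already due, so a pre-dose test is easy to do. The longer ages above rest on assumed gaps, while 4.4 asks for a prompt start and for delays to be discussed with the Principal Investigator. Finally, 5.6 concerns later testing and has no bearing on the first dose.

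Much of this stands. The protocol does not allow dosing without any test, 3.2.10 governs, the 10-day figure needs a one-week delay, and the 5.6 point is separate. What does not follow is that the calendar is right. It names a looser, differently anchored test as the one that clears the patient for treatment, and even with no gap at all it accepts a test three times as old as 3.2.10 does. That a careful site can reconcile the texts is a reason to rate the point low, not to leave it.

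**Conclusion.** The concern holds, at low severity. One safety requirement is stated in two ways that differ in length and anchor, and the calendar carries the weaker form with no Cycle 1 mark and no window in its footnote to correct it. A test that meets the calendar note can be at least 2 days older than 3.2.10 allows, and older by each further day between enrollment and dosing. The 2-day minimum excess follows from the text alone; anything above it depends on the assumed gap and on whether the general 7-day baseline limit is read as applying. How often sites would act on the calendar alone cannot be judged from the documents. Separately, 5.6 and footnote 9 disagree on how often to test during the study. Neither point touches an endpoint, the DLT rule or any statistical quantity.

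**What to change.** - Reword the calendar note and footnote 9 to require a negative test no more than 24 hours before the first dose of blinatumomab, in addition to any screening test.
- Add a Cycle 1 Day 1 pre-dose mark to the HCG row of Table 10.1.
- In 5.6, cite footnote 9 (a test before each cycle) as the minimum on-study frequency and leave institutions free to test more often.

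The first two changes bring the maximum test age at first dose to 24 hours wherever a site looks. The cost is three wording edits and one table mark. No test is added beyond those that 3.2.10 and footnote 9 already require.
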